8.3.10. Combined Piromelatine Treatment Group 20 mg + 50 mg vs Placebo

An additional exploratory efficacy analysis will be carried out for the primary and secondary efficacy endpoints (as detailed in Sections [4.1](#) and [4.2](#)) comparing placebo with a combined treatment group of 20 mg + 50 mg.

These analyses will be performed on the full analysis set using the MMRM model and will include calculation of an effect size. See [Section 8.1](#) and [8.2](#) for the individual analyses.

8.3.11. ApoE4 Carrier Status

An additional exploratory efficacy analysis will be carried out for all primary and secondary efficacy endpoints (as detailed in Sections [4.1](#) and [4.2](#)) separately for ApoE4 carriers and non-carriers (as described in [Section 7.5](#)).

These analyses will be performed on the full analysis set using the MMRM model and will include calculation of an effect size. See Sections [8.1](#) and [8.2](#) for the individual analyses.

These analyses will be performed only for patients who have provided their consent to use their genetic material for the analysis of the ApoE gene.

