3.6. DETERMINATION OF SAMPLE SIZE

Eligible patients will be enrolled equally in a 1.2:1:1:1 randomization ratio to the 4 trial arms (placebo [1.2] and the equal piromelatine treatment arms 5 mg, 20 mg, and 50 mg [1:1:1]). Assuming an effect size between treatment dose and placebo of 0.35 over 26 weeks, a significant level (α) of 0.05 for one-sided test, and power of 80%, a sample size

of 115 patients for the placebo arm and 95 for each of the 3 piromelatine arms is calculated. Assuming a 50% screen failure rate and allowing for 15% patient withdrawal, 920 patients should be screened in order to randomly assign 460 patients, of whom it is expected 400 will complete the study. Enrollment will end on November 30th 2018.

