8.3.12. Insomnia at Baseline

An additional exploratory efficacy analysis will be carried out for all primary and secondary efficacy endpoints (as detailed in Sections [4.1](#) and [4.2](#)) separately for patients with and without insomnia as determined by the PSQI score obtained at baseline (as described in [Section 7.5](#)).

These analyses will be performed on the full analysis set using the MMRM model and will include calculation of an effect size. See Sections [8.1](#) and [8.2](#) for the individual analyses.

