8.3.13. Alzheimer's Disease Medications at Baseline

An additional exploratory efficacy analysis will be carried out for all primary and secondary efficacy endpoints (as detailed in Sections [4.1](#) and [4.2](#)) separately for patients receiving Alzheimer's disease medications (acetylcholinesterase inhibitors and/or memantine) and naïve patients (as described in [Section 7.5](#)).

These analyses will be performed on the full analysis set using the MMRM model and will include calculation of an effect size. See Sections [8.1](#) and [8.2](#) for the individual analyses.

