Additional analyses: For the purpose of increasing the statistical power the 20 mg and 50 mg arms will be combined to create an active arm with larger sample size for an analysis as compared to placebo. This active versus placebo analysis will be applied to all endpoints for the FAS using the MMRM.

As the paper-based CFT/COWAT and computerized OBK of the cNTB executive function domain are collected differently, an exploratory analysis shall be performed, where the analyses on the cNTB global composite score shall be repeated with the paper-based components removed as detailed in [Section 8.3.9](#).

Additional subgroup exploratory analyses will be performed, as detailed in Sections [8.3.11 - 8.3.13](#), to explore the subgroup effects for ApoE4 carriers, insomnia at baseline and AD concomitant medications.

Prior medications: Section 17.3.1 of the protocol states that prior medications will be summarized by treatment group, but prior medications will be listed only.

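### The ApoE4, insomnia and AD-medication analyses report each stratum separately, and no planned output estimates the difference in treatment effect between strata

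*SAP*

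**What the plan says.** Three exploratory subgroup analyses cover all primary and secondary efficacy endpoints. Section 8.3.11 runs them "separately for ApoE4 carriers and non-carriers". Section 8.3.12 runs them "separately for patients with and without insomnia as determined by the PSQI score obtained at baseline". Section 8.3.13 does the same for patients on Alzheimer's medication and those not on it ("acetylcholinesterase inhibitors and/or memantine) and naïve patients"). Section 6.6 gives the common rule: the MMRM in the full analysis set, plus Cohen's d.

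Each section points back to Sections 8.1 and 8.2. The MMRM there contains treatment by visit and baseline by visit as its only interactions, and ApoE4 enters as a covariate without a treatment interaction. Its outputs are adjusted mean differences from placebo with standard error, 95% CI and P value. CGIC is the exception: Section 8.2.1 uses a van Elteren test.

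Section 10 lists these analyses as additions to the protocol, made "to explore the subgroup effects for ApoE4 carriers, insomnia at baseline and AD concomitant medications". The index of tables (Section 14) names by-visit and MMRM tables for each factor (by-visit only for CGIC). No title refers to a contrast between strata.

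**The concern.** A subgroup effect is a difference in treatment effect between strata. The plan gives two separate estimates per factor, each tested against zero, and stops there. A significant result in one stratum beside a non-significant one in the other is not evidence that the effects differ. With arms sized for a single overall comparison, that pattern is common even when the effect is the same in everyone. At stake is how the exploratory results are read, not the primary conclusion.

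**Working it through.** **Inputs from SAP Section 3.6.** Effect size: "Assuming an effect size between treatment dose and placebo of 0.35 over 26 weeks". Test: "of 0.05 for one-sided test, and power of 80" per cent. Numbers: "115 patients for the placebo arm and 95 for each of the 3 piromelatine arms". Allocation: "1.2:1:1:1 randomization ratio to the 4 trial arms".

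**Assumptions.** The share f of patients in the larger stratum is not in the SAP; I use 50% to 80%. A single standardised two-sample comparison (SD = 1) stands in for the MMRM. Strata are independent and both arms split in the same proportion.

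**Step 1: reproduce the SAP's figure.** Placebo n = (1 + 1.2) × (1.645 + 0.842)² / 0.35² = 111.03, rounded up to 112, with about 94 per active arm. For 115 against 95, SE = √(1/115 + 1/95) = 0.1386, so 0.35/0.1386 = 2.525 and one-sided power is Φ(2.525 − 1.645) = 81%. The stated 80% is reproduced. At two-sided 0.05, the level matching the planned 95% CIs, power is Φ(2.525 − 1.960) = 71%.

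**Step 2: power within each stratum under a uniform effect.** The stratum SE is 0.1386/√f or 0.1386/√(1 − f). At 50:50 it is 0.196, so power = Φ(0.35/0.196 − 1.960) = Φ(−0.175) = 43%.

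**Step 3: chance that exactly one stratum is significant.** This is p₁(1 − p₂) + p₂(1 − p₁). At 50:50: 2 × 0.431 × 0.569 = 0.490.

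| Split (assumed) | Power, larger / smaller stratum | Exactly one significant, two-sided 0.05 | Same, one-sided 0.05 |
|---|---|---|---|
| 50:50 | 43% / 43% | 49% | 49% |
| 60:40 | 50% / 36% | 50% | 50% |
| 70:30 | 56% / 28% | 53% | 54% |
| 80:20 | 62% / 20% | 57% | 59% |

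Noncentral-t values differ by about one percentage point (52% at 70:30).

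**Step 4: several factors and doses.** The primary endpoint alone has 3 factors × 2 strata × 3 doses = 18 within-stratum tests, or 9 factor-by-dose pairs. I simulated 3,000 trials per setting with a uniform effect of 0.35, three independent factors, a shared placebo arm, two-sided 0.05 and splits of 50% to 70%. At least one of the three factors was discordant for a given dose in 74% to 77% of trials, and at least one of the nine pairs in 96% to 97%.

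**Step 5: the direct contrast.** A treatment-by-subgroup test at two-sided 0.05 flags a uniform effect 5% of the time by construction (simulated 4.3% to 6.0%). Its SE is 0.1386 × √(1/f + 1/(1 − f)): 0.277 at 50:50 and 0.347 at 80:20. Power to detect 0.35 in one stratum against 0 in the other is 24% at 50:50 and 17% at 80:20.

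**The case against.** A reader might infer that the SAP means to declare a subgroup effect whenever one stratum is significant and the other is not. It does not say so. The analyses are labelled exploratory, Section 10 speaks only of exploring, and no decision rule appears. The 49% to 57% is therefore a rate of discordant P values, not of planned false claims. It also depends on a real uniform effect of 0.35. With no effect at all, exactly one stratum is significant in favour of piromelatine in about 2 × 0.025 × 0.975 = 5% of cases.

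A reader might also infer that the planned outputs cannot address the question. That goes too far. The MMRM reports a difference, SE and CI in each stratum, and the strata contain different patients. An approximate contrast can be formed by hand, with SE = √(SE₁² + SE₂²). The CIs mislead less than the P values: at 50:50 with a uniform effect, both estimates favour piromelatine with probability Φ(1.785)² = 93%, and the two 95% CIs fail to overlap in only about 0.6% of cases (z = 2 × 1.960/√2 = 2.77). The contrast is unreported rather than unobtainable. Nor does the SAP say that these results will guide patient selection in a later trial.

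Two further objections stand in part. The count of 18 tests is a multiplicity matter that an interaction test does not remove; nine contrasts remain. And interaction power is low. That is a reason to report the estimate and interval, not to omit them.

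Section 6.5 mentions an interaction term, but leaves it undefined and uses it for residual checks, so it does not fill the gap. The table shells are separate attachments and were not available; the point rests on the SAP text and its table index.

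**Conclusion.** The point holds as a reporting gap. The only planned subgroup analyses are within-stratum, and nothing in the SAP text or table index estimates the difference that Section 10 sets out to explore. Under a uniform effect of 0.35 with 115 against 95 patients, comparing stratum P values would show an apparent difference in about half of cases per factor and dose. That holds for any assumed split from 50:50 to 80:20. ApoE4 genotyping is optional, so those strata may be smaller and less powerful than shown. The figures do not model the repeated measures. The primary test is unaffected. I class this as a cheap improvement.

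**What to change.** For each factor and each MMRM endpoint, also fit one model with subgroup, treatment-by-subgroup and treatment-by-subgroup-by-visit terms. Use the full analysis set, or, for ApoE4, those of its patients who consented to genotyping, as Section 8.3.11 requires. For each dose, report the between-stratum difference in treatment effect with its 95% CI and interaction P value beside the stratum estimates, and add this to the tables in Section 14.

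For CGIC, where the MMRM does not apply, either present the stratum results descriptively or use an ordinal model with a treatment-by-subgroup term.

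State in Section 6.6 that stratum P values alone will not support a subgroup claim, and that a non-significant interaction does not show a uniform effect.

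The cost is one extra model per factor and endpoint, on data already planned for collection. Because interaction power is low, the CI carries most of the information and the results stay exploratory.

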8.3.12. Insomnia at Baseline

An additional exploratory efficacy analysis will be carried out for all primary and secondary efficacy endpoints (as detailed in Sections [4.1](#) and [4.2](#)) separately for patients with and without insomnia as determined by the PSQI score obtained at baseline (as described in [Section 7.5](#)).

These analyses will be performed on the full analysis set using the MMRM model and will include calculation of an effect size. See Sections [8.1](#) and [8.2](#) for the individual analyses.

8.3.13. Alzheimer's Disease Medications at Baseline

An additional exploratory efficacy analysis will be carried out for all primary and secondary efficacy endpoints (as detailed in Sections [4.1](#) and [4.2](#)) separately for patients receiving Alzheimer's disease medications (acetylcholinesterase inhibitors and/or memantine) and naïve patients (as described in [Section 7.5](#)).

These analyses will be performed on the full analysis set using the MMRM model and will include calculation of an effect size. See Sections [8.1](#) and [8.2](#) for the individual analyses.

8.3.14 Clinical Dementia Rating

The Clinical Dementia Rating (CDR) data will be listed only.

9. SAFETY

The safety analysis set will be used for the listing of safety data and for all safety analyses. Safety will be assessed on the basis of adverse event (AE) reports, clinical laboratory data (including sex hormones), ECG parameters, physical examinations, vital signs and suicidal ideation (Sheehan-STS).

9.1. EXTENT OF EXPOSURE

The duration of exposure (in days) to study medication will be summarized using summary statistics for continuous variables. This will be calculated using the safety analysis set.

Duration of exposure will be calculated by:

$$\text{Date of last dose} - \text{date of first dose} + 1$$

The study medication accountability will be listed along with the duration of exposure.

9.3. ADVERSE EVENTS

Adverse events will be collected throughout the study, from informed consent until the end of the treatment period.

Adverse events will be summarized by the SOC and PT based on the MedDRA dictionary version 17.1 or later.

Treatment emergent adverse events (TEAEs) are defined as any adverse events (AEs) that occur after the start of administration of the first dose of study drug and through

14 days after the last dose of study drug, or any event that is present at baseline and continues after the first dose of study drug but worsens in intensity.

See Section 14.1 of the protocol for definition of serious adverse events (SAEs).

Treatment emergent AEs will be characterized based on the onset date relative to each patient's participation in the study.

Adverse events with incomplete start dates will be considered a TEAE if:

- Day and month are missing and the year is equal to or after the year of the first dose date;
- Day is missing and the year is after the year of the first dose;
- Day is missing and the year is equal to the year of the first dose date and the month is equal to or after the month of the first dose date;
- Year is missing; or
- Complete date is missing.

If the relationship to study treatment is missing then related will be used for the summaries. Similarly, events with missing intensity or severity will be counted as severe (Grade 3).

The summary tables will include the number of subjects and the number of events. Percentages will be based on the number of subjects. For summaries by SOC and PT, a patient will be counted once at the SOC level and once at each PT within the SOC level. For summaries by SOC, PT, and maximum severity, a patient will be counted once at the highest severity level for which the event occurred at the SOC level and the highest severity level for each unique PT within that SOC level. Therefore, patients may only contribute once to each PT and once to each SOC level.

The summaries presenting frequency of AEs by SOC and PT will be ordered by overall descending frequency of SOC and then, within a SOC, by overall descending frequency of PT.

The following AE tables will be provided:

- An overall summary of the number and percentage of patients reporting AEs, TEAEs, treatment-related TEAEs, severe TEAEs, serious TEAEs, treatment-related serious TEAEs, and TEAEs leading to withdrawal of study medication;
- TEAEs, overall and by SOC and PT;

- Serious TEAEs, overall and by SOC and PT;
- TEAEs related to study medication, overall and by SOC and PT;
- TEAEs, overall and by SOC, PT and maximum severity;
- TEAEs leading to withdrawal of study medication, overall and by SOC and PT;
- TEAEs, overall and by PT;
- All AEs, overall and by SOC and PT;
- All AEs, overall and by SOC, PT and maximum severity.

With the exception of the all AEs table, only the TEAEs will be included in the summary tables; however, all AEs will be included in the listings. Any AE occurring during the single-blind run-in, before the first dose of study medication in the double-blind treatment phase, will be included in the summaries of all AEs only. Any AE occurring before the single-blind run-in will be included in the data listings but will not be included in the summary tables of AEs. Any AE occurring within the defined 14 day follow-up period after discontinuation of study medication will be included in the AE summaries.

With the exception of the all AEs tables, the summaries of TEAEs will present frequency of AEs by SOC and PT, will be ordered by overall descending frequency of SOC and then, within a SOC, by overall descending frequency of PT.

An additional listing will be provided for SAEs leading to withdrawal from the study. TEAEs will be flagged in the listings.

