7.6. PRIOR AND CONCOMITANT MEDICATIONS

A summary of medications taken during the course of the study will be presented in tabular form using Anatomical Therapeutic Chemical (ATC) classification level 2 and PT via the World Health Organization Drug Classification Dictionary (WHO-DD) version March 2012 or later. All medications will be summarized using the full analysis set by treatment group and sorted alphabetically by ATC level 2 class and PT.

Prior medications are those medications taken before the start of treatment in the single-blind run-in phase, not including medications ongoing at the start of the run-in. A medication is considered concomitant in the single-blind run-in phase if ongoing at or taken on or after the start date of treatment in the run-in. A medication is considered concomitant in the double-blind treatment phase if ongoing at or taken on or after the start date of study treatment. A medication can be concomitant in both the single-blind run-in and double-blind treatment phases. Concomitant medications will be summarized by the number and percentage of patients taking a particular medication using the coding described above by phase. If a patient has taken a medication more than once, the patient will be counted only once in the total. Prior medications will be listed only.

See Section 12.9 of the protocol for more details on the time frame allowed for medications.

All prior and concomitant medications will be listed on the safety analysis set by treatment group.

Medications with incomplete end dates will be considered concomitant, unless an incomplete date (e.g. month and year) clearly indicates that the medication started and stopped prior to the start of treatment:

- Day and month are missing and the year is equal to or after the year of the start of treatment in the run-in;

- Day is missing and the year is after the year of the start of treatment in the run-in;
- Day is missing and the year is equal to the year of the start of treatment in the run-in and the month is equal to or after the month of the start of the run-in;
- Year is missing; or
- Complete date is missing.

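### The TEAE rule for incomplete start dates ignores the stop date, so an adverse event known to have ended before the first double-blind dose can be counted as treatment emergent

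*SAP*

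**What the plan says.** All of the following is in SAP Section 9.3 unless stated.

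- **Collection.** "Adverse events will be collected throughout the study, from informed consent until the end of the treatment period". Screening and run-in events are therefore in the database.
- **Definition.** A TEAE is "any adverse events (AEs) that occur after the start of administration of the first dose of study drug and through" a cut-off two weeks past the final dose, or an event present at baseline that continues past the first dose and worsens. Section 6.2 places that first dose at Week 0 (Visit 2), which follows the 2-week single-blind run-in described in Section 3.4.
- **Basis.** "Treatment emergent AEs will be characterized based on the onset date relative to each patient's participation in the study".
- **Partial dates.** "Adverse events with incomplete start dates will be considered a TEAE if" one of five conditions is met. One of them is "Day and month are missing and the year is equal to or after the year of the first dose date". Another, for a start date that lacks only its day, is a known month in the first-dose year that is no earlier than the first-dose month. The others are a missing day with a later year, a missing year, and a wholly missing date. None refers to the stop date.
- **Run-in events.** "Any AE occurring during the single-blind run-in, before the first dose of study medication in the double-blind treatment phase" is assigned to the all-AE summaries and to no other summary. Events from before the run-in are to be listed but kept out of the AE summary tables.

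Section 6.3 sends missing AE dates to Section 9.3 and adds no further rule. For medications, Section 7.6 has an exception where an incomplete date "clearly indicates that the medication started and stopped prior to the start of treatment".

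**The concern.** Treating an event as treatment emergent when its timing is unknown is a reasonable cautious default. Here the timing is not unknown: a stop date before the first double-blind dose settles that the event was over before randomised treatment began. The list in Section 9.3 does not use that information. The same section then gives two answers for one event, TEAE by the partial-date list and not TEAE by the definition and the run-in sentence.

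At stake is the accuracy of the TEAE tables. A misplaced event counts in the overall TEAE summary and the SOC/PT tables. Because Section 9.3 also sets a missing relationship to related and a missing severity to severe, a poorly documented pre-dose event could enter those tables as well.

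**Working it through.** The SAP states no figure on this point, so there is none to reproduce. The check applies the five conditions as written to events that start and stop before the first double-blind dose.

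**1. Worked example (assumed dates).** First double-blind dose 20 June 2017; the run-in therefore starts on 6 June; the event runs from 8 to 12 June, and the stop date is fully recorded.

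| What is missing from the start date | Condition applied | Result |
|---|---|---|
| Day | 2017 = 2017 and June = June | TEAE |
| Day and month | 2017 = 2017 | TEAE |
| Year | year missing | TEAE |
| Whole date | date missing | TEAE |

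By the definition, the event did not occur after 20 June, and it did not continue past 20 June and worsen. It is not a TEAE. By the run-in sentence it belongs in the all-AE summaries only. The partial-date list gives the opposite result in all four rows.

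**2. Not every such event is caught.** Let the first dose be on 5 June, with a run-in event from 24 to 28 May and only the start day missing. May is before June, so no condition is met and the event is correctly left out.

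**3. Share of resolved run-in events that the rule flags.** Assumptions: first-dose dates spread evenly over the 365 days of 2017, onset uniform over the 14 days before the first dose, and every event ended before that dose. There are 365 × 14 = 5,110 combinations.

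- *Day missing.* The event escapes only if onset falls in the calendar month before the first dose. For first-dose days 1 to 14 of a month, 14 + 13 + … + 1 = 105 combinations do so. Over 12 months that is 12 × 105 = 1,260. Flagged: (5,110 − 1,260)/5,110 = 3,850/5,110 = 0.753.
- *Day and month missing.* The event escapes only if onset falls in the previous year, which is possible for first doses on 1 to 14 January: 105 combinations. Flagged: (5,110 − 105)/5,110 = 0.979.
- *Year missing, or whole date missing.* Always flagged: 1.000.

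A 30-day month gives the same first result: the mean over d = 1 to 30 of min(d − 1, 14)/14 is (105 + 210)/(14 × 30) = 0.75.

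**4. With a stop-date condition added.** Every event in this exercise has a stop date before the first dose, so the share flagged is 0 in all four cases.

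**5. Effect on comparisons between arms.** Let p be the true proportion of patients with a TEAE in an arm, and e the proportion given a false one, the same in every arm and independent of true TEAEs. The observed proportion is p + e(1 − p). The difference between active (p₁) and placebo (p₀) becomes (p₁ − p₀)(1 − e). For small e it is almost unchanged; ratios move slightly toward 1.

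**The case against.** The strongest reply is that Section 9.3 already handles this. The run-in sentence covers any AE in the run-in, makes no exception for partial dates, and agrees with the TEAE definition. On that reading the five conditions are only a fallback for uncertain timing. This shows what the authors meant, but the SAP does not say that the run-in sentence takes precedence, or that stop dates are used to place an event. The list is the explicit algorithm, and a programmer who codes it as written will set the flag.

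It can also be said that the rule is conservative, in line with the defaults for missing relationship and severity. That is true: the error over-reports harm and hides none. It lowers the importance but does not make the classification right. Query resolution before database lock (Section 2.2) should reduce the number of incomplete dates further, and that point stands.

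A reader might infer more than the document supports:

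- *That the 75% measures the defect.* It does not. The same share would apply to any run-in event with a missing day, including those that continue past the first dose or have no informative stop date, where the cautious default is defensible. Only events whose stop date proves earlier resolution are misclassified, and their number is not given.
- *That the comparison with placebo is compromised.* Section 9.3 plans counts and percentages with no test between arms, and the rule applies alike in every arm.
- *That TEAE incidence is the main tolerability endpoint.* Section 4.4 lists adverse events among seven safety variables and ranks none above the others.
- *That Section 7.6 contains the same rule with the safeguard in place.* That rule deals with incomplete end dates of medications. It shows a similar principle and is only a loose parallel.

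**Conclusion.** The point holds as a minor specification defect. The partial-date list in Section 9.3 can make a TEAE of an event whose recorded stop date lies before the first double-blind dose, against both the definition and the run-in sentence of the same section. It affects only events with an incomplete start date and an informative stop date. They are probably few, although the SAP gives no number. Within that class the rule misclassifies about 75% to 100% of resolved run-in events, depending on which part of the date is missing, given uniform onset over the 14 days and evenly spread first-dose dates. The consequence is a slight over-count of TEAEs that does not depend on arm. No efficacy conclusion and no planned test is affected.

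**What to change.** Add one sentence to the partial-date rule in Section 9.3: an AE with an incomplete start date is not a TEAE if its stop date, or the known part of it, shows that it ended before the first double-blind dose; otherwise the listed conditions apply. Events whose timing is truly uncertain then stay TEAEs. Events known to have resolved in the run-in go to the all-AE summaries, and those known to have resolved before the run-in go to the listings only, as the section already intends.

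The cost is that sentence and one extra condition in the derivation of the TEAE flag. It needs no new data, and it leaves the rule unchanged for events without an informative stop date.
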